We hypothesize that preterm infants supplemented with early physiologic doses of L-carnitine while on parenteral nutrition will have improved short-term growth parameters and significantly higher neurobehavioral scores when compared with control infants.

Primary Aims:

To determine whether carnitine supplementation is associated with:

- 1. Decreased percent weight loss within the first two weeks of life and decreased length of time to regain birthweight.
- 2. Improved performance on the NICU Network Neurobehavioral Scale (NNNS) at 40 weeks postmenstrual age (+/- 2 weeks).

Secondary Aims:

To determine whether carnitine supplementation is associated with:

- 1. Increased rate of growth of head circumference within the first month of life and increased food efficiency (weight gain/calorie intake) during the supplementation period.
- 2. Normalization of the serum carnitine profile at two weeks of life, compared with infants born at a post-menstrual age 2 weeks later.
- 3. Enhanced brain maturation as measured by amplitude-integrated EEG (aEEG) measurements obtained during the hospital course
- 4. Fewer abnormal findings, better brain growth, white matter development and brain metabolism on brain magnetic resonance imaging (MRI) at 36-40 weeks' corrected age (prior to hospital discharge)

Because of the potential for systemic effects of L-carnitine supplementation, we will also monitor those variables which showed significant difference in our prior study: rates of proven infection, hearing screen failure and PDA ligation.

Primary Outcomes:

- 1. Length of time to regain birthweight,
- 2. Percent weight loss in the first two weeks of life,
- 3. Neurodevelopmental scores on the NICU Network Neurobehavioral Scale (NNNS) at 40 weeks post-menstrual age (+/- 2 weeks)

Methods/Design:

This is a prospective, randomized controlled clinical trial involving infants with gestational age (GA) <32 wks who are born at either the Jack D. Weiler Hospital or the Wakefield Division of Montefiore and admitted to theirNeonatal Intensive Care Unit. Informed consent will be obtained from the parents of eligible patients as early as possible within 72 hours of birth. Infants whose parents have signed an informed consent form will be randomized to receive either carnitine supplementation (50 µmol/kg/day) versus placebo within 72-96 hours of birth.

Inclusion criteria:

- Infants born <32weeks' gestation
- Exclusion criteria:
 - Presence of

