 - o potentially life-threatening congenital anomaly
 - o known hereditary metabolic disorder
 - o known chromosomal abnormality
 - teratogen exposure with symptomatic substance withdrawal
 - o congenital viral infections
 - microcephaly
 - Grade IV intraventricular hemorrhage (IVH) or seizures documented within first 72 hours of birth
 - Critically-ill with life expectancy less than 72 hours
 - Unable to obtain consent within 72 hours of birth
 - Enrolled in another intervention trial

Participant recruitment: Parents or guardians of infants who meet study criteria will be approached regarding the study as early as possible within 72 hours of the infant's birth. Informed consent will be obtained by study investigators and coordinators. Permission will be requested to re-contact the families after completion of the supplementation study for follow-up.

Randomization: As previously described by Pande et al., enrolled patients will be randomized to either the treatment group (L-carnitine, 50 µmol/kg/day) or placebo group (5% glucose, similar volume as the L-carnitine group).²⁸ Patients who meet study entry criteria and have signed informed parental/guardian consent will be enrolled in the study. Because gestational age and small for gestational age (SGA) status will impact our outcome measures, we will ensure they are equally distributed in the arms of the study by stratifying based upon these variables. We will analyze the two study arms using an intent-to-treat analysis. Therefore, enrolled patients will be stratified into fourgroups: gestational age 23 to 26 6/7 weeks, gestational age 27 to 29 6/7weeks, gestational age 30 to 31 6/7 weeks and small for gestational age (SGA). Patients within each stratum will be randomized by the pharmacist using a computerized block-generation with sets of 4. In the case of multiple births, all infants must meet study criteria, and the infants will be randomized as a set. One infant of the multiple-birth set will be randomly chosen for inclusion in the analysis. A recruitment log of all screened infants will be maintained. Clinicians and the nursing staff will be unaware of the arm of the treatment protocol to which the patient is assigned. Codes will be unblinded only after all patients have reached the study end-point, or at the request of the Data Safety Monitoring Board.

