Study supplementation: Infants randomized to the treatment group will receive 50 µmol/kg/day of Lcarnitine intravenously for 2 weeks, and infants randomized to placebo will received 5% glucose, similar volume to the L-carnitine group. At two weeks, sufficient carnitine is provided in enteral feeds of either breast milk or infant formula. If no intravenous access is available before the supplementation endpoint, the equivalent dose of enteral study supplement (L-carnitine or placebo) will be administered.⁴¹ Parenteral and enteral nutrition will be provided according to standard NICU protocol.

Of note, as many as 10% of the infants in the study will likely continue to rely primarily on parenteral nutrition beyond the proposed two-week supplementation period. Enteral feeds may be withheld from these infants due to underlying illnesses such as sepsis or gastrointestinal disorders like necrotizing enterocolitis. Due to the presence of underlying illness, these infants are at an even higher risk for developing developmental delays.⁴²Therefore, in study patients who are not receiving adequate enteral nutrition (100 cc/kg/day of enteral intake) after 2-weeks of study supplements, carnitine supplementation will be continued until these infant are receiving adequate enteral feeds; at this point, their physiologic carnitine requirements will be met by enteral nutrition alone.

Timeline of Assessments:

- a. Within 72 hours of birth
 - i. Patient enrollment and initiation of study protocol

- ii. Initial carnitine panel drawn
- iii. Initial aEEG reading obtained within 2-3 days of study initiation
- iv. Study Supplement begins within 72-96 hours of birth
- b. Two weeks after study initiation
 - i. Study Supplement concludes (in a small sub-set of patients, study supplementation will be continued until enteral feeds reach 100 cc/kg/day)
 - ii. Follow-up carnitine panel drawn (in addition, as blood transfusions may impact carnitine levels, serum carnitine profiles will be drawn prior to blood transfusion administered between the first and second weeks of life)
- c. aEEG readings will be obtained within 2-3 days of study initiation and at the following post-menstrual ages: 28 weeks (if infant <27 weeks at birth), 32 weeks', 36 weeks', and at 40 weeks' (if infant is still admitted to the NICU).
- d. 36-38 weeks' corrected age
 - i. Cranial MRI
- e. 40 weeks GA (+/- 2weeks)
 - i. Neurodevelopmental assessment

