- 1. Patient demographics: date of birth, birth weight, gestational age as determined by best obstetric estimate or Ballard score, SGA or LGA status, Apgar scores, birth history, delivery room management, gender, ethnicity.
- 2. Maternal characteristics: maternal age, maternal language, ethnicity, presence of prenatal care, type of insurance coverage, maternal educational status, presence of maternal depression, teratogen exposure (alcohol, tobacco or illicit drug use during pregnancy), antenatal steroid use, hypertension/pre-ecclampsia, gestational diabetes/Type I or II diabetes, and maternal infections.
- 3. Management of fluid and nutrition: daily fluid intake and urine output, glucose infusion rate, total caloric intake, total protein intake, and food efficiency (weight gain divided by caloric intake) while on study supplement.
- 4. Hospital course:
 - a. Growth parameters: weight, length and head circumference at birth, daily weight until birthweight regained and then weekly, weekly length, and head circumference two times per week for four weeks)
 - b. Cardiovascular: need for vasopressors, presence of PDA (including medical or surgical treatment; platelet count and mean fluid intake at time of treatment)
 - c. Gastrointestinal: feeding intolerance, NEC, presence of gastrointestinal reflux,
 - Neurological: results of aEEG readings, results of head ultrasounds including presence of germinal matrix/intraventricular hemorrhage and periventricular leukomalacia, cranial MRI results
 - e. Opthalmological: grade of retinopathy of prematurity and treatment or ophthalmologic diagnosis,
 - f. Hematologic: transfusion history including dates
 - g. Infectious disease: presence of concurrent presumed and proven infection,
 - h. Other: performance of any surgical procedures, duration of intravenous access, use of medications, and hearing screen results (OAE and/or ABR) with observed thresholds of hearing frequencies.
 - i. Clinical Risk Index for Babies (CRIB) scores will be calculated for each infant.
 - j. We will also monitor for possible short-term side effects.
- 5. Discharge information: weight, length, head circumference, and diagnoses at time of discharge, routinely-ordered discharge brain MRI findings
- 6. Neurodevelopmental assessment:

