These aEEG recordings are non-invasive and do not create additional risk for the patient. These aEEG readings will be performed by study personnel and will be provided at no additional cost to the patient.

MRI Brain Imaging

Imaging of the brain at term-equivalent is the standard of care for the evaluation of preterm infants prior to being discharged home. In our Neonatal Intensive Care Units, we routinely obtain brain MRI at \geq 36 weeks' corrected age (prior to discharge home). The MRI examination is performed in sleeping infants after they have been fed; therefore, sedation is not required for the procedure. MRI will be performed per routine protocol at 36 weeks' corrected age, prior to discharge home. Brain growth will be assessed on anatomical images, through manual segmentation of the basal ganglia, cerebellum and whole brain. White matter development will be assessed on diffusion tensor imaging (DTI), using the tract-based spatial statistics method. The DTI measures fractional anisotropy and mean diffusivity, which have previously been shown to be abnormal in ex-preterm children; these will be compared in multiple white matter regions (cerebral peduncle, posterior limb of the internal capsule, corona radiata, corpus callosum, and optic radiations).^{37,46,47}

Brain metabolism will be assessed using proton MR spectroscopy, obtained from both white matter (centrum semiovale) and gray matter (basal ganglia) structures. The relative concentrations of the brain metabolites choline, creatine and n-acetylaspartate (NAA) will be compared between control and carnitine-supplemented children. Each metabolite reflects specific cellular and biochemical processes. NAA is a neuronal marker and decreases with any disease that adversely affects neuronal integrity. Choline is a constituent of cell membranes and an intermediate of phospholipid metabolism. Choline levels on MR spectroscopy increase with increased membrane turnover, and are taken as a measure of cell proliferation. Creatine plays a role in maintaining energy-dependent systems in brain cells by serving as a reserve for high energy phosphates. Because the creatine peak remains fairly stable even in face of disease, it may be used as a control value.⁴⁸ In children born preterm, the NAA/Choline ratio at term-equivalent age correlates with later cognitive development.⁴³

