The effect of L-carnitine supplementation on outcome measures in enrolled infants will be examined for significance by comparing the two groups using unpaired data analysis with the assistance of a statistician. Continuous data (percent weight loss, time to regain birthweight, NNNS score, BSID-III scores) will be compared between the "placebo" and the "carnitine supplemented" groups by unpaired student t-test (a 2 tailed P value <0.05 will be considered to indicate statistical significance) or Wilcoxon's rank sum test for non-parametric parameters. Unmatched nominal data will be compared using Fisher's Exact Test or Chi-square test as required (e.g.: presence or absence of normalization of the carnitine profile; or presence or absence of pathological findings on the discharge MRI). Logistic regression models will be used to adjust for potentially confounding factors including gestational age, birth weight, race, gender, Apgar scores.

Risks and Discomforts:

A brief description of the risks and discomforts associated with this study is included in the protocol consent form and will be discussed in detail with each family at the time of study enrollment.

Carnitine is routinely administered with parenteral nutrition in approximately one-third of the neonatal intensive care units in the United States, although not in the Jack D. Weiler Hospital or Montefiore North Division NICU's. Carnitine is FDA-approved, and there have been no reports of severe toxicity from

overdose. Data available from the adult literature reports side effects of mild gastrointestinal symptoms such as gastritis, vomiting, diarrhea or abdominal cramping; body odor; and seizures, in patients with or without a known seizure disorder. These side effects are dose-dependent and might be avoided by slow consumption of the solution or greater dilution. One investigator reported transient elevation of triglycerides and increased platelet aggregation in uremic patients with severe renal insufficiency who received high doses of carnitine supplementation.⁵²

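### The binary MRI comparison in secondary aim 4 takes no account of haemorrhage present before the first dose; stratifying by pre-dose ultrasound status is a cheap gain in precision.

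*Combined protocol and SAP*

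**What the plan says.** Secondary Aims, item 4, looks for "Fewer abnormal findings, better brain growth, white matter development and brain metabolism on brain magnetic resonance imaging (MRI") near term-equivalent age. For the abnormal-findings part, the only test given is under Outcome Measures. There "presence or absence of pathological findings on the discharge MRI" is an example of nominal data to be compared by Fisher's exact or chi-square test. The plan does not define a pathological finding and does not separate lesions present before dosing from later ones.

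On haemorrhage at entry, the exclusion criteria list "Grade IV intraventricular hemorrhage (IVH) or seizures documented within first 72 hours of birth". Grades I to III are not excluded. The Timeline of Assessments states "Study Supplement begins within 72-96 hours of birth", so a bleed found in the exclusion window precedes that start.

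The Randomization paragraph stratifies by three gestational-age bands and SGA status. Baseline Comparability lists race, sex, prenatal care, multiple gestation and type of delivery as its categorical comparisons. The logistic models are to "adjust for potentially confounding factors including gestational age, birth weight, race, gender, Apgar scores". Early haemorrhage is named in none of these places. The Data collection section does capture "results of head ultrasounds including presence of germinal matrix/intraventricular hemorrhage and periventricular leukomalacia".

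**The concern.** The hypothesis is neuroprotection by a supplement given from about day 3. A haemorrhage that occurred earlier cannot have been prevented by it. If such a lesion is still visible and read as pathological at the discharge scan, the infant is abnormal in either arm. Two things follow. The difference between arms shrinks, because part of each arm cannot respond. The share of infants with early lesions will also differ between arms by chance, which adds noise to the MRI comparison. Stratifying by gestational age and SGA removes only the part of that noise that those factors predict. A baseline variable strongly related to this outcome, on which some data are already collected, is left unused.

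**Working it through.** The plan gives no MRI abnormality rate, effect size or power. Its sample-size statement (50 per arm) covers the primary outcomes only, so there is no MRI figure to reproduce. What follows is an illustration.

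**Inputs**
- n = 50 scanned per arm: the plan's desired 100 infants, assumed all scanned.
- q = share with a pre-dose lesion: assumed 20%, range 10% to 30%.
- New abnormality in other infants: assumed 30% on placebo and 15% on carnitine (a halving).
- r = probability that a pre-dose lesion by itself leaves the discharge MRI abnormal: assumed 100%, 75%, 50% or 25%. Otherwise that infant has the same new-abnormality rate as the rest.

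**Dilution at q = 20%, r = 100%**
- Placebo: 0.2 + 0.8 × 0.30 = 0.44. Carnitine: 0.2 + 0.8 × 0.15 = 0.32.
- The difference is 12 points rather than 15. The relative reduction is 0.12/0.44 = 27% rather than 50%.
- Unstratified: z = 0.12/√(0.44×0.56/50 + 0.32×0.68/50) = 1.25.
- Stratified: the lesion stratum is all abnormal and carries no information, leaving 40 per arm. z = 0.15/√(0.30×0.70/40 + 0.15×0.85/40) = 1.63.
- Equivalent sample ratio: the squared ratio of the unrounded z values (1.633 and 1.246) is 1.72.

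**The same at r = 75%**
- Lesion stratum: placebo 0.75 + 0.25×0.30 = 0.825; carnitine 0.75 + 0.25×0.15 = 0.7875.
- Overall: placebo 0.2×0.825 + 0.8×0.30 = 0.405; carnitine 0.2×0.7875 + 0.8×0.15 = 0.2775; difference 0.1275.
- Unstratified: z = 0.1275/√(0.405×0.595/50 + 0.2775×0.7225/50) = 1.36.
- Stratified, strata weighted by size: variance = 0.8²×(0.21+0.1275)/40 + 0.2²×(0.1444+0.1673)/10 = 0.00665, so z = 0.1275/√0.00665 = 1.56.
- Ratio about 1.33.

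**Equivalent sample gain from stratifying**

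| r | q = 10% | q = 20% | q = 30% |
|---|---|---|---|
| 100% | 1.36 | 1.72 | 2.08 |
| 75% | 1.18 | 1.33 | 1.43 |
| 50% | 1.08 | 1.13 | 1.17 |
| 25% | 1.02 | 1.03 | 1.04 |

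**Chance imbalance at q = 20%**
- 95% range for the difference in lesion prevalence: ±1.96×√(2×0.2×0.8/50) = ±15.7 points.
- Infants without a lesion are abnormal 30% or 15% of the time anyway. At r = 100%, a lesion therefore raises the chance of an abnormal MRI by 0.70 or 0.85.
- Shift in the MRI difference: 15.7×0.70 = 11.0 to 15.7×0.85 = 13.3 points, about the size of the 12-point effect.
- An imbalance of 10 points or more has probability about 0.26 by simulation.

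**Validity and power**
- Simulation with no treatment effect and r = 100% gave a mean difference of 0.00 and a type I error of 0.050 to 0.057 for q from 0 to 30%.
- At q = 20%, r = 100% and two-sided 0.05, power is 0.23 counting all infants and 0.36 in the 40 per arm without a pre-dose lesion. With no pre-dose lesions at all it would be 0.43.

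**The case against.** The case for leaving the plan alone has several parts.

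- **Scope.** The binary comparison is one example in a multi-part secondary aim with no power claim. MRI Brain Imaging also plans continuous measures: "Brain growth will be assessed on anatomical images, through manual segmentation of the basal ganglia, cerebellum and whole brain", and "White matter development will be assessed on diffusion tensor imaging (DTI), using the tract-based spatial statistics method", plus spectroscopy. This stands and limits the weight of the point. However, those measures address other parts of aim 4, and no other test is given for abnormal findings.
- **Definition.** A reader might infer that every Grade I-III bleed counts as a treatment failure. The documents do not say so. Pathological is undefined, and a bleed may have resolved by the time of the scan. This stands, and it is why r is varied above.
- **Adjustment.** A reader might infer that early haemorrhage will never be adjusted for. The covariate list is open-ended, and it includes gestational age and birth weight. The accurate statement is that haemorrhage is not named. An open list, though, leaves the choice until after the data are seen.
- **Bias.** A reader might infer that the comparison is biased. It is not: randomisation balances early lesions on average, and the test already allows for chance imbalance. The loss is in precision.
- **Data.** The case report form entry mentions presence of haemorrhage but specifies neither grade nor date, while nearby items specify grade for retinopathy and dates for transfusions. No pre-dose ultrasound is scheduled. This also stands. The fix needs a small addition to data capture and will not be complete for every infant.

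**Conclusion.** The point holds as a cheap improvement to one secondary comparison. The documents support four facts: Grade I-III haemorrhage before the first dose is compatible with entry; such a lesion may make the discharge MRI abnormal in either arm; the stated test is unadjusted; and early haemorrhage is not a stratum, a listed baseline comparison or a named covariate. The consequence is dilution and noise.

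The size depends on rates that the documents do not give. At 20% prevalence, the gain from stratifying runs from about 1.7 times the sample, if all pre-dose lesions leave the MRI abnormal, to near 1.0 if a quarter do. The largest gain in the table, 2.08, needs both 30% prevalence and r = 100%, so it is an upper edge and not an expectation. Precision improves or roughly holds in every case examined. Even in the favourable 20% case, the comparison remains underpowered for a halving of new abnormality.

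**What to change.** Make these changes before unblinding.

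1. Under Outcome Measures, compare abnormal MRI between arms with a Cochran-Mantel-Haenszel or exact test. Stratify by haemorrhage status on the last head ultrasound before the first dose: none or not done / Grade I-II / Grade III. If grade is not recorded, use present v absent.
2. Name the same variable in the logistic model for this outcome.
3. On the case report form, record the date and grade of head ultrasounds already performed. Tie the variable to each infant's actual first-dose time, because the Individual Infant Timeline places dosing within 24 hours of enrolment while the Timeline of Assessments gives 72-96 hours.
4. Do not define new lesions by comparing ultrasound with MRI. The two methods differ in sensitivity, so a lesion could look new only because MRI detects it.

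The cost is a few lines of analysis text, one derived variable and two data fields. No procedure is added and every scanned infant stays in the analysis. The downside is that infants with no pre-dose ultrasound share a category with those who had a normal one. Undetected bleeds may sit there and reduce the gain.

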These measurements will be obtained through brain MRIs routinely obtained in preterm infants prior to discharge. There will be no change in the routine protocol in order to obtain these outcomes. The reading and analyses of these MRIs will be performed at no additional cost to the study subject.

Neurobehavioral Assessment:

Infants discharged from the Weiler and Montefiore North Division NICUs routinely follow-up with our neonatologists at term-equivalent age. At this visit, the infants routinely receive a neurobehavioral

assessment. We have chosen to administer the NICU Network Neurobehavioral Scale due to its prevalence of use in neonatal research and its strong psychometric properties.⁴⁹

The NICU Network Neurobehavioral Scale (NNNS) was developed by [name]., & [name].⁵⁰ The scale is intended for use with use with healthy and at-risk preterm infants and full term infants at risk because of prenatal substance exposure or other conditions. The NNNS can be utilized in either a clinical or research setting in order to obtain a comprehensive assessment of neurobehavioral functioning. There is a focus on neurologic, stress, and withdrawal signs. The tool may be used with infants through 6 weeks of age and may be used as early as 30 weeks for preterm infants. The exam assesses 115 items in three categories:

- Neurological items: active and passive muscle tone, primitive reflexes, and central nervous system integrity
- Behavioral state, sensory, and interactive responses
- Stress/abstinence items

The examiner assesses the items. Summary scores are generated for stress, withdrawal, and the major domains of neurobehavioral performance. The NNNS is administered in a standardized format which allows objective assessment of the infant. Normed scores are available for at-risk and healthy infants. Because the assessment is relatively new, there are no long-term studies looking at predictive validity. However, the test is based upon a variety of prior tools, where long-term predictive validity has been shown.⁵¹ The test takes approximately 20 minutes to administer. (Ordering information: http://www.brookespublishing.com/store/books/lester-7659/index.htm)

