The DSMB will review all adverse events as described in the Charter. All unanticipated problems will be reported to the DSMB and IRB within 5 days of the PI becoming aware of the problems.

With the upcoming revisions in the IRB AE reporting policy, we have decided to not follow the current IRB adverse event reporting policy dated 2008; instead we will report AEs to the IRB as follows:

- 1. Unanticipated Problems defined as anyevent, deviation, or problem
 - thatmeetsallofthefollowingcriteria:
 - unanticipated; AND
 - possibly,probablyordefinitelyrelatedto studyparticipation;AND
 - fatal,life-threatening,orseriousORsuggestsgreaterriskofharmtostudy participant(s)or othersthanwaspreviouslyknownorrecognized
- 2. Deathofaparticipantifitoccurswithin30 daysofadministrationofthestudymedication
- 3. AProtocolDeviation or an incident, experience,oroutcomethatmayplacetheparticipantorothersatgreatermedical, physiological,socialriskoreconomicriskthanwaspreviouslyknownorrecognized
- 4. AnydeviationfromIRBorInstitutionalPolicyorProcedurewhichhasthepotentialto adverselyimpactoneormoresubjectsortheoverallintegrityofdatacollected
- 5. AnyreportingthattheIRBcitesasaconditionofapprovaloftheprotocol
- 6. Complaintfromaparticipantorotherindividualwhenthecomplaintindicates unexpectedrisksorthecomplaintcannotberesolvedbytheresearchteam

- 7. DeviationfromtheIRBInformedConsentPolicy
- 8. Systematicdatacollectionerrors
- 9. Breachofconfidentiality

It is well-known that the very preterm, low birth weight infants included in this study have increased mortality compared to full-term infants. Review of our own Weiler NICU data in 2010 revealed a high mortality rate ininfants less than 30 weeks gestational age: approximately 75% for infants of gestational age of 23 weeks, 24% for gestational age 24-26 weeks, and 5% for infants of gestational age 27 – 29 weeks. Thus, we expect similar rates in infants enrolled in our study.

An additional amount of blood will be drawn as part of the study protocol. The estimated amount of blood is approximately $200 - 300 \mu$ I two to three times over the course of the study. The blood draw will be obtained with other routine bloodwork whenever possible in order to avoid additional discomfort to the infant.

Benefits:

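### The abnormal-MRI comparison for secondary aim 4 scores only infants who survive to the routine pre-discharge scan, and the plan does not say how deaths before the scan are counted

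*Combined protocol and SAP*

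**What the plan says.** - **Outcome and test.** Secondary Aims, item 4, includes fewer abnormal findings on brain MRI. Under Statistical Analyses, Outcome Measures, the nominal version is "presence or absence of pathological findings on the discharge MRI", compared between arms by Fisher's exact or chi-square test.
- **Source of the scan.** The MRI Brain Imaging section states: "MRI will be performed per routine protocol at 36 weeks' corrected age, prior to discharge home". It adds: "These measurements will be obtained through brain MRIs routinely obtained in preterm infants prior to discharge", and "There will be no change in the routine protocol in order to obtain these outcomes". No scan after discharge is planned.
- **Scan window.** This varies: 36-40 weeks in Secondary Aims and the Individual Infant Timeline, "36-38 weeks' corrected age" in the Timeline of Assessments, and both 36 weeks and 36 weeks or later under MRI Brain Imaging.
- **Expected deaths.** Risks and Discomforts reports the unit's 2010 mortality as about 75% at 23 weeks, "24% for gestational age 24-26 weeks" and 5% at 27-29 weeks, and expects similar rates in the trial. It gives no figure for 30-31 weeks.
- **Analysis principle.** The Randomization paragraph promises intent-to-treat. No section says how an infant who dies before the scan, or who survives without one, enters the MRI comparison.

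**The concern.** A binary outcome that can be read only in infants alive at 36 weeks or later is conditioned on an event after randomisation. An infant with severe brain injury who dies at two weeks is not counted as abnormal; that infant leaves both numerator and denominator. If one arm loses more of its brain-injured infants, its scanned survivors look healthier. The arm with more deaths could then look better on an outcome meant to show brain protection.

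Selection that acts alike in both arms does not bias the comparison. The problem needs an arm difference in survival. The protocol does not predict one, but its own background leaves room for one in either direction: it reports fewer proven infections and more PDA ligations on carnitine in the earlier trial.

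**Working it through.** The plan gives no sample size, power or expected rate for the MRI outcome, so it has no figure of its own to reproduce.

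**1. Infants unscored because of death**

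Formula: dead fraction = sum over gestational-age bands of (enrolment share × mortality). Mortality comes from Risks and Discomforts: 0.75, 0.24 and 0.05. Enrolment shares and mortality at 30-31 weeks (0% or 5%) are assumptions. All deaths are taken to precede the scan. The 150 is the planned recruitment under Sample size.

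| Assumed shares: 23 / 24-26 / 27-29 / 30-31 weeks | 0% mortality at 30-31 weeks | 5% mortality at 30-31 weeks |
|---|---|---|
| 2% / 13% / 30% / 55% | 6.12% (9.2 of 150) | 8.87% (13.3) |
| 0 / one third / one third / one third | 9.67% (14.5) | 11.33% (17.0) |
| 1/12 / 3/12 / one third / one third | 13.92% (20.9) | 15.58% (23.4) |
| 10% / 35% / 35% / 20% | 17.65% (26.5) | 18.65% (28.0) |

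First cell: 0.02×0.75 + 0.13×0.24 + 0.30×0.05 + 0.55×0 = 0.0150 + 0.0312 + 0.0150 = 0.0612. The range is about 6% to 19%, or 5 to 14 infants per arm of 75.

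**2. Effect on the scanned-only comparison if survival differs**

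All inputs here are assumed: deaths 12% on placebo and 6% on carnitine; 30% abnormal among the 88% who would survive in either arm, so carnitine has no true effect on lesions; 80% abnormal among the extra 6% who survive only on carnitine.

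- Placebo, scanned: 0.30.
- Carnitine, scanned: (0.88×0.30 + 0.06×0.80) / 0.94 = (0.264 + 0.048) / 0.94 = 0.332.
- Spurious difference: 3.2 points against carnitine.

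With the survival assumption swapped between arms, the same arithmetic gives 3.2 points in favour of carnitine, the arm that would then have twice the deaths.

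**3. Size against sampling error**

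With 75 randomised per arm, scanned numbers are 75×0.88 = 66 and 75×0.94 = 70.5.

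- SE = √(0.30×0.70/66 + 0.332×0.668/70.5) = √(0.00318 + 0.00315) = 0.080.
- Shift / SE = 0.032 / 0.080 = 0.4.
- A two-sided 5% test shifted by 0.4 SE rejects with probability P(Z > 1.56) + P(Z < −2.36) = 0.059 + 0.009, about 7%.

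Fewer scanned infants would enlarge the SE and make the shift smaller relative to it.

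**4. Same inputs, deaths counted**

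- Placebo, death or abnormal: 0.12 + 0.264 = 0.384.
- Carnitine, death or abnormal: 0.06 + 0.264 + 0.048 = 0.372.

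**5. Equal survival**

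If carnitine does not change who survives, the extra 6% disappears. Both scanned groups show 30% and the difference is 0.

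**The case against.** **Nobody predicts a survival effect, and the distortion is small.** The hypothesis concerns growth and neurobehaviour. The differences reported from the earlier trial are in infection, hearing screens and PDA ligation, not mortality. The example needs deaths to halve, and even then moves the result by 0.4 SE. This stands, and it limits the point to a modest one.

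**The plan already adjusts and stratifies.** Randomisation is stratified by gestational age and SGA status, and logistic regression will adjust for gestational age, birth weight and Apgar scores. This may absorb part of the selection, but it gives no outcome to an infant who died and cannot remove selection on brain injury itself.

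**Enrolled infants may die less often than the 2010 rates imply.** Grade IV haemorrhage or seizures within 72 hours, and life expectancy under 72 hours, are exclusions. That is fair, though the protocol says it expects similar rates.

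**Three stronger readings are tempting, and the documents do not support them.**

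- *Selection at both ends of severity, because the healthiest infants go home unscanned.* An infant discharged before 36 weeks would indeed have no score. But no section says this happens or gives a rate. MRI Brain Imaging describes the scan as routine before discharge, and the Individual Infant Timeline places NICU discharge after 36 weeks.
- *The analysis can reverse the sign of aim 4.* In the example the true lesion effect is zero, so there is no sign to reverse. The 1.2-point advantage on the composite (38.4% − 37.2%) comes from the assumed difference in deaths.
- *Ultrasound could fill the gap.* The case report form lists "results of head ultrasounds including presence of germinal matrix/intraventricular hemorrhage and periventricular leukomalacia", but with no schedule and no statement that every infant has one. The last ultrasound might precede study supplementation. If it is less sensitive than MRI, the arm with more ultrasound-scored infants would look healthier, which adds a bias.

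**Conclusion.** The gap is real but modest. The binary MRI outcome is defined only for infants who reach the pre-discharge scan, and the intent-to-treat promise has no rule to carry it out for those who die. The size of the unscored group, roughly 6% to 19%, rests on the protocol's mortality rates and on assumed gestational-age mixes.

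Bias arises only if survival differs by arm. The shift of about 3 points illustrates the mechanism under assumed inputs and is not a forecast. The outcome is one measure under a secondary aim, with no power claim attached. No primary outcome or sample-size figure depends on it. The change is worth making because it is cheap and because a rule chosen after unblinding would be hard to defend.

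**What to change.** In Outcome Measures:

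- Pre-specify death before the scan or abnormal MRI, by arm, among all randomised infants in the analysis set (one infant per multiple-birth set, as the plan already provides). Report it beside the scanned-only Fisher or chi-square comparison, with death and abnormal MRI also shown separately.
- Report by arm the number without an MRI and the reason: death, discharge before the scan, or other.
- For survivors without a scan, give simple bounds: all counted normal, then all counted abnormal. With 75 infants per arm, each such infant widens that arm's bounds by 1/75 = 1.3 points.
- Do not substitute the last cranial ultrasound for a missing MRI.
- Reconcile the differing MRI windows, so that death before the scan has one meaning.

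The cost is SAP wording and one derived variable from data already recorded; no extra scan or visit is needed. The downside is that the composite mixes mortality with imaging, which is why the scanned-only result stays in the report.
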